8.2 Image processing

Image processing will be done at OHSU.

8.2.1 For CNS lesions:

SS-CBV maps will be created using the high resolution T2*w scans before and after contrast agent and $\Delta R2^*$ maps will be created using the formula $\Delta R2^* = \ln(SI_{pre}/SI_{post})/TE$, in which SI_{pre} and SI_{post} indicate the signal intensities pre- and post ferumoxytol, and TE is the echo time. DSC-CBV maps from gadoteridol DSC will be created using a mathematical leakage correction method in NordicICE (Nordic Neurolab, Bergen, Norway) an FDA approved perfusion MRI software (if gadoteridol could not be given per institutional protocol (see protocol below) ferumoxytol enhancement will be used). The coregistration and overlay of CBV maps on T1-w MPRAGE will be done using NordicICE as well [27, 33]. The clinical MR sequences, such as T1 weighted scans with and without gadoteridol, and T2 weighted pre contrast scans will also be read. Images will be read by 2 radiologists. The radiologists will be blinded to the type of CBV maps (SS and DSC) and subject information.

8.2.2 Oregon Health & Science University policy on assessment of lab results prior to gadolinium based contrast media

For patients with the following risk factors, a serum creatinine level will be obtained with calculation of eGFR according to the following guidelines:

- 1) Creatinine/eGFR NOT required:
 - Dialysis patients – No eGFR required
 - Dialysis patients are excluded from the requirements in numbers 2 and 3 below.
- 2) Creatinine/eGFR required within 24 hours of MRI scan:
 - All inpatients (includes Daypatients and ER patients)
 - Outpatients whose most recent eGFR<60
- 3) Creatinine/eGFR required within 30 days of MRI scan:

- Patients >60 years of age
- Outpatients with a history of hypertension requiring medication
- Outpatients with diabetes mellitus
- Outpatients with kidney disease: kidney transplant, single kidney, kidney cancer, kidney surgery
- Outpatient children < 1 year of age

The technologist or RN will notify the radiologist for the following:

- 1) Patient has a history of NSF (Nephrogenic Systemic Fibrosis)
- 2) Patient is on dialysis
- 3) Patients with eGFR <30 mL/min/1.73m²
- 4) Patient received gadolinium based contrast media within the past 24 hours
- 5) For questions related to kidney function or patient history

Informed Consent: The radiologist will obtain informed consent and document risk/benefit of procedure in the patient's medical record for any of the following patients who will be receiving IV gadolinium-based contrast:

- 1) Patients with eGFR<30
- 2)) Patients on dialysis

8.2.3 For systemic lesions (only Arm 1).

With immunotherapy treatment, an increase in total tumor burden of previously stable systemic lesions (tumor flare reaction) has been described [92]. Based on the location of the systemic lesions, and the feasibility of MR imaging, subjects in Group 1 (melanoma) will be offered optional MR imaging of systemic lesions, to evaluate response as part of the exploratory endpoints. Only subjects with measureable, but stable, systemic involvement at the time of enrollment, will be considered for this imaging. Subjects must provide additional consent for this optional portion of the study.

Fractional Blood Volume (fBV), Vessel Size Index (VSI), and Vessel Density Index (VDI) values will be obtained by defining a region of interest over the entire tumor area. This process will be repeated for 3 central slices of the tumor for every lesion, and the mean value within the region of interest (ROI) will be calculated. T2 and T2* values will be obtained, using GRE and SE data respectively, by plotting mean ROI value at each echo, and calculating the best-fit exponential decay function. R2 and R2* will be defined as the inverse of T2 or T2* values; DR_2 , DR_2^* will be calculated as the ratio of values before and after iron contrast injection.

Fractional Blood Volume of the tumor was derived from the relationship of DR_2^* , fractional blood volume (fBV) and magnetic field constants (g , B_0) to changes in magnetic susceptibility, D_c .

$$D_c = \frac{3}{4\rho} \frac{DR_{2,muscle}^*}{fBV_{muscle}gB_0} = \frac{3}{4\rho} \frac{DR_{2,tumor}^*}{fBV_{tumor}gB_0}$$

$$\frac{3}{4\rho} \frac{DR_{2,muscle}^*}{fBV_{muscle}gB_0} = \frac{3}{4\rho} \frac{DR_{2,tumor}^*}{fBV_{tumor}gB_0}$$

$$fBV_{tumor} = fBV_{muscle} \frac{DR_{2,tumor}^*}{DR_{2,muscle}^*}$$

where fBV_{muscle} is assumed to be a constant of 3%.

Vessel Size Index will be computed using the following equation:

$$VSI = 0.424 \left(\frac{ADC}{gD_c B_0} \right)^{1/2} \frac{DR_2^*}{DR_2}$$

For normalized value calculations, the first two terms will be considered to be constant for all images and will be therefore disregarded.

Vessel Density Index was computed as follows:

$$VDI = 329 \frac{DR_2}{DR_2^*}$$

As for the VSI calculations, the first term in the VDI equation will be disregarded during calculation of normalized values.

Paramagnetic maps will also generated by calculating VSI,VDI and fBV values on a voxel-by-voxel basis. Histograms will be obtained by plotting vessel indices within a tumor region-of-interest against the frequency of occurrence.

Data will be reported as fBV, VSI and VDI +/- standard error of the mean.

8.3 Tumor Tissue Collection and Correlative Blood Biomarker Studies

8.3.1 Blood Biomarkers - Optional

- Correlate clinical and radiological response with systemic immune responses using multicolor flow cytometry, measuring total T-cells (CD3+) with CD4/CD8 ratio,
- T-Reg (CD4+/CD127-/bright CD25+), DNT (CD3+/CD4-/CD8-), Naïve T (CD3+/CD45RA+), memory T (CD3+/CD45RO+), T-cell activation (CD3+/variable CD69+/variable CD25+/variable HLA-DR), NK and NK-activation (CD3-/CD56+/variable CD16+), total B-cells (CD19+), naïve B-cells (CD19+/IgD-/CD27-), memory B-cells (CD19+/IgD-/CD27+).
- Blood will be collected ± 15 days of each ferumoxytol MRI scan. These timepoints are: at baseline, at 4 weeks after the last day of radiation, at suspicion of radiographic progression, and 4 weeks after suspected radiographic progression. All timepoints ± 15 days.
- Blood samples will be collected at OHSU and processed at the OHSU research laboratory.

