2.0 TRIAL DESIGN

This study will evaluate incidence, magnitude and timing of true vascular tumor progression, pseudoprogression and immune response to pembrolizumab in patients with primary brain tumors using ferumoxytol steady state MRI imaging.

Originally, the study had two arms:

ARM 1: Metastatic brain tumors - Metastatic melanoma

ARM 2: Primary brain tumors - Glioblastoma (GBM)

In December 2019, we decided to stop the enrollment to the melanoma arm and allocate the remaining 18 slots to the Glioblastoma arm – a total of 43 subjects will now be enrolled in the GBM arm.

Treatment

Subjects scheduled to receive standard of care stereotactic radiosurgery (SRS) for brain metastases in Arm 1 or standard of care chemoradiation (CRT) with temozolomide for GBM in Arm 2, are eligible. All subjects will receive pembrolizumab (200mg intravenous every 3 weeks) in addition to standard of care SRS or CRT in the respective arms, until toxicity, or persistent radiographic progression is confirmed, whichever comes first.

Imaging

All subjects will be scanned with clinical MRI at baseline prior to radiation, 4 weeks after the last day of radiation and every 9 weeks thereafter until completion or until taken off-study for

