progression or toxicity. Ferumoxytol MRI (FeMRI) will be performed in the same day and sitting as the clinical MRI at baseline and 4 weeks after the last day of radiation timepoints. FeMRI may be performed independently (on a different day or different MRI setting) of the clinical MRI if there is suspected radiographic progression or to confirm radiographic progression. If there is suspected progression, subjects undergo a ferumoxytol steady state MRI and continue on pembrolizumab for one more cycle. The decision regarding continuation of pembrolizumab will be made by the principle investigator based on clinical findings that include (1) stable ECOG performance status with no more than 8mg of dexamethasone (or equivalent) a day; (2) absence of new or worsening symptoms not managed with steroids; and (3) absence of progressive tumor at critical anatomical sites (e.g., spinal cord compression) requiring urgent alternative medical intervention. Follow up clinical standard of care and ferumoxytol MRIs will be repeated to confirm persistent radiographic progression in 4 weeks. During this 4 week follow up period, subjects will be followed with a clinical exam weekly to monitor for clinical stability. If the 4 week follow up scan confirms progression (as defined in section 8.1), then pembrolizumab is discontinued and subject is evaluated for clinical indication of standard of care surgery or biopsy. Surgery or biopsy is performed only if 1) the lesion is deemed easily accessible 2) surgery is not expected to worsen neurological outcomes and 3) it is in the best clinical interest of the subject. The decision regarding surgery will be consensus based and when possible, will be made after each individual case has been presented at the OHSU multi-disciplinary brain tumor board. If histopathology confirms pseudoprogression or is inconclusive, the subject will continue on pembrolizumab every 3 weeks until further radiographic progression is suspected. If histopathology confirms progression, the subject will be removed from the study. Subjects with evidence of new lesions distant from the primary lesion/s (not present at entry to the study) in the CNS or systemically that fulfil criteria for progression by immune related response criteria (irRC)[1] will be taken off study drug, but will be followed with serial clinical standard of care MRI.

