4.3.2 Rationale for Dose Selection/Regimen/Modification

Pembrolizumab

An open-label Phase I trial (Protocol 001) is being conducted to evaluate the safety and clinical activity of single agent MK-3475. The dose escalation portion of this trial evaluated three dose levels, 1 mg/kg, 3 mg/kg, and 10 mg/kg, administered every 2 weeks (Q2W) in subjects with advanced solid tumors. All three dose levels were well tolerated and no dose-limiting toxicities were observed. This first in human study of MK-3475 showed evidence of target engagement and objective evidence of tumor size reduction at all dose levels (1 mg/kg, 3 mg/kg and 10 mg/kg Q2W). No MTD has been identified to date. 10.0 mg/kg Q2W, the highest dose tested in PN001, will be the dose and schedule utilized in Cohorts A, B, C and D of this protocol to test for initial tumor activity. Recent data from other clinical studies within the MK-3475 program has shown that a lower dose of MK-3475 and a less frequent schedule may be sufficient for target engagement and clinical activity.

PK data analysis of MK-3475 administered Q2W and Q3W showed slow systemic clearance, limited volume of distribution, and a long half-life (refer to IB). Pharmacodynamic data (IL-2 release assay) suggested that peripheral target engagement is durable (>21 days). This early PK and pharmacodynamic data provides scientific rationale for testing a Q2W and Q3W dosing schedule.

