6.0 SCHEDULE OF EVENTS

	Screening visit: within 28 days of first treatment	Pembro infusion every 3 weeks +15 days	At suspected radiographic progression (+15 days)	At persistent radiographic progression (+15 days)	Safety follow-up: 30 days (+15 days) post discontinuation of pembro	Follow-up: those who complete 2 years of treatment or 35 cycles	Survival: follow-up once off study ⁸
Informed Consent	X						
Inclusion/Exclusion Criteria	X						
Archival Tissue Collection (if available)	X						
Standard of Care Biopsy or Resection of Brain Lesion ¹				X			
Demographics and Medical History	X						
Medication, herbal or dietary supplement review	X		X	X	X	X	
Review Adverse Events, include Events of Clinical Interest ¹⁰			X	X	X	X	
Physical Examination ²	X			X	X	X	
Vital Signs and Weight	X			X	X	X	
ECOG Performance Status	X			X	X	X	
CBC with Differential ³	X	X			X		
Comprehensive Serum Chemistry Panel (with LDH) ³	X	X			X		
Urinalysis	X						
FT4 and TSH ⁴	X	X			X		
PT/INR, aPTT	X				X		
Pregnancy Test (urine or serum/males only – see section 7.6)	X						
Clinical Tumor Imaging	X ⁵					X ⁷	
Ferumoxytol imaging	X ⁶						
24 hr post study drug MRI - Optional	X ⁶						
Biomarker Collection (serum) Optional	X ⁶						
Post-study anticancer therapy status						X	
Survival Status						X	X
Telephone contact							X ⁸

¹Subjects must undergo standard of care biopsy or maximal safe resection as clinically indicated prior to enrollment.

²Physical exam required with every pembrolizumab infusion.

³CBC and CMP (with LDH) to be done every 3 weeks while on pembrolizumab - labs must be done within 28 days before first pembrolizumab infusion, and within 72 hours of subsequent pembrolizumab infusions. Additional labs may be drawn at treating physician's discretion.

⁴FT4 and TSH with every cycle while on pembrolizumab.

⁵Clinical standard of care MRIs are done at baseline, 4 weeks after the last day of radiation and then every 9 weeks (see special instructions below for evaluating persistent radiographic progression). Clinical MRIs may be done more often at physician's discretion.

⁶Ferumoxytol steady state MRIs (within 7 days of clinical standard of care MRIs) are done baseline, 4 weeks after the last day of radiation, anytime there is suspected radiographic progression and 4 weeks after suspected radiographic progression (all timepoints ± 15 days). Serum biomarkers will be obtained ± 15 days of ferumoxytol MRI scan.

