⁷ Follow-up after completing 2 years of treatment or 35 cycles (whichever comes later): according to standard of care.

⁸ Survival follow-up once off study: Telephone contact every 12 weeks (± 30 days) to assess for survival status until death, withdrawal of consent, the end of the study, or loss to follow-up, whichever occurs first.

¹⁰Adverse event review will be recorded in Epic continuously while on study. A separate Epic note will be done with each course. All AEs are assessed for attribution to pembrolizumab, ferumoxytol, and standard of care therapy

Trial treatment with pembrolizumab will start on the first day of standard of care radiation (± 15 days) and thereafter every 3 weeks (± 15 days) (dosing delays of up to 7 days are permitted at physician discretion for medical / surgical events or logistical reasons) for up to 2 years or 35 cycles or confirmed radiographic progression, whichever occurs first. Dosing interruptions (missing a dose) are permitted in the case of medical / surgical events or logistical reasons not related to study therapy (e.g., elective surgery, unrelated medical events, subject vacation, and/or holidays), not to exceed two consecutive doses or a maximum of 9 weeks.

Imaging instructions for evaluating persistent radiographic progression: if there is suspected progression, subjects undergo a ferumoxytol steady state MRI and continue on pembrolizumab for one more cycle (total of 4 weeks). At the 4 week point, clinical standard of care and ferumoxytol MRIs will be repeated to confirm persistent radiographic progression. If the 4 week scan confirms progression, then pembrolizumab is discontinued and subject is evaluated for surgery. If histopathology confirms pseudoprogression or is inconclusive, the subject will continue on pembrolizumab every 3 weeks until further radiographic progression is suspected. If histopathology confirms progression, the subject will be removed from the study. If the subject is not a surgical candidate, they will be taken off study and move into the survival follow up stage.

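### The optional baseline immune blood sample may be drawn after treatment has begun, so it is not assured to be an untreated reference

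*Combined protocol and SAP*

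**What the plan says.** Section 8.3.1 sets the blood window ("Blood will be collected ± 15 days of each ferumoxytol MRI scan") and names the scans it covers: "These timepoints are: at baseline, at 4 weeks after the last day of radiation, at suspicion of radiographic progression", and then the scan 4 weeks after suspicion. Baseline has no rule of its own. Footnote 6 to the Schedule of Events (section 6.0) agrees: "Serum biomarkers will be obtained ± 15 days of ferumoxytol MRI scan".

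The anchor scan is placed by section 2.0: "All subjects will be scanned with clinical MRI at baseline prior to radiation", and "Ferumoxytol MRI (FeMRI) will be performed in the same day and sitting as the clinical MRI at baseline". No minimum gap between that scan and treatment is given. The schedule's screening column is headed "Screening visit: within 28 days of first treatment".

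On the start of treatment, section 6.0 states: "Trial treatment with pembrolizumab will start on the first day of standard of care radiation", with a tolerance of 15 days either side.

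Section 7.6 includes the serum biomarker assay in its list of laboratory tests, with a pointer to section 8.3.1. Below Table 5 it asks for screening laboratory tests within 10 days before the first dose.

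The blood data serve exploratory objective 2 (section 3.3), which relates clinical and radiological response to the systemic immune response to pembrolizumab. Section 3.4 expects the immune blood markers to be up-regulated at various time points.

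**The concern.** An immune response to pembrolizumab, or an up-regulation of blood markers, can only be judged against a value taken before pembrolizumab. Here the blood window is two-sided at baseline as at every other scan, and the baseline scan may fall close to the start of treatment. A sample can therefore satisfy the protocol, be labelled baseline, and still have been taken under checkpoint blockade, during chemoradiation, or both. Section 4.3.2 itself describes target engagement in the periphery lasting beyond 21 days on an IL-2 release assay, so a draw within two weeks of a dose is not a neutral one.

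The plan takes more care with tissue: for exploratory objective 3, section 10.0 compares values from before pembrolizumab with values at progression. Nothing equivalent is written for blood. At most 43 glioblastoma subjects can contribute, and fewer if some decline the optional draw, so a few mislabelled samples would count.

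**Working it through.** The plan states no figure on this point to reproduce. The check is calendar arithmetic on the stated windows.

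**Inputs**
- Blood window: scan day − 15 to scan day + 15 (section 8.3.1; footnote 6).
- Baseline scan: before radiation, no minimum gap (section 2.0); screening window 28 days (section 6.0).
- First pembrolizumab: radiation day 1, ± 15 days (section 6.0).

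**Set-up.** Let day 0 be the first radiation day, the scan be on day −s (s ≥ 1), and the first pembrolizumab dose be on day p, with p from −15 to +15. The latest permitted baseline draw is on day 15 − s. It falls after radiation start if 15 − s > 0, and after the first dose if 15 − s > p.

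| First dose (day p) | Scan (day −s) | Latest draw (day 15 − s) | Days after first dose (15 − s − p) |
|---|---|---|---|
| 0 | −1 | +14 | 14 |
| 0 | −7 | +8 | 8 |
| 0 | −14 | +1 | 1 |
| 0 | −15 | 0 | 0 |
| 0 | −21 | −6 | −6 (before dose) |
| −15 | −1 | +14 | 29 |
| −15 | −14 | +1 | 16 |
| +15 | −1 | +14 | −1 (before dose) |

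**Dose on day 0.** Scans 1 to 14 days before treatment, which are 14 of the 28 days in the screening window, permit a draw after both the first dose and the start of radiation. A scan 15 days before permits a draw on day 0. From 16 days on, the whole window lies before treatment.

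**Dose on day −15.** The lag after the first dose reaches 14 − (−15) = 29 days, past the nominal second dose at 21 days. This case needs a scan that follows the first dose. Section 2.0 permits that because it ties the scan only to radiation. If the screening column is taken to require the scan before the first dose as well, the latest scan is on day −16, the latest draw is on day −1, and the lag is −1 − (−15) = 14 days.

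**Dose on day +15.** With s ≥ 1 the draw stays before the first dose, but it can still be 14 days into radiation.

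**Later pair of samples.** With scans exactly 28 days apart and ± 15 days on each draw, the interval between samples runs from 28 − 15 − 15 = −2 days to 28 + 15 + 15 = 58 days. The scans' own tolerances would widen this. The reversed order needs both draws at opposite extremes.

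**With the fix.** If the baseline draw must precede both the first dose and the first fraction, the largest permitted lag after treatment start is 0 days. No sample size or error rate changes.

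**The case against.** Two places can be read as already requiring an untreated sample. The biomarker mark sits in the screening column, but its footnote covers all four scans and repeats the ± 15 days, so the column does not confine the draw. The 10-day rule in section 7.6 is stronger, since the biomarker assay is in the same laboratory list. That entry points back to section 8.3.1, however, where the wider window stands. It is therefore fair to say that the text is unreconciled, but not that a pre-treatment draw is assured.

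It can also be said that the sample is optional, the objective exploratory, and the analysis a search for preliminary signals. All of that is true, and it limits the weight of the point. Section 10.0 correlates blood parameters with response and tumor size; it specifies no change-from-baseline analysis for blood and does not say which time point enters.

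Some stronger readings are tempting but not supported:

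- **Baseline blood will be contaminated.** This depends on the scan-to-treatment gap and on when staff actually draw.
- **The change from baseline is biased toward zero.** That needs the early change to run in the same direction as the later one. Checkpoint blockade, chemoradiation and steroids may pull differently, and the documents give no early effect on any marker in the flow-cytometry panel. The IL-2 assay result does not supply one.
- **Section 8.3.1 stacks a second 15 days on the first.** Its closing sentence reads more naturally as the scan tolerance or a repeat.
- **A known share of samples is late.** With the dose on day 0 and draws uniform over the window, the late share is the average of (15 − d)/30 over the gap d, taken as 0 beyond 15 days. For gaps uniform on 0–7 days it is (15 − 3.5)/30 = 38%; on 0–14 days, (15 − 7)/30 = 27%; on 0–28 days, (112.5/30)/28 = 13%. Nothing in the documents supports uniform timing, so these figures only illustrate how much the answer depends on the assumption.

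**Conclusion.** The point holds as a statement of what the windows permit. Sections 8.3.1 and 6.0 allow a baseline draw up to 14 days after radiation start, and up to 14 days after the first dose when dosing begins with radiation. The 29-day figure rests on two further conditions: dosing 15 days before radiation, and a baseline scan tied only to radiation. A sample drawn that late is not an untreated reference for exploratory objective 2 or for the expectation in section 3.4. How often this occurs, and in which direction and by how much it would distort results, cannot be determined from the documents. No primary or secondary endpoint, sample size or safety rule is affected. This is an inexpensive improvement, not a flaw in the main design.

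**What to change.** - In section 8.3.1 and footnote 6, require the baseline biomarker draw before both the first pembrolizumab dose and the first radiation fraction. Bring the laboratory timing in section 7.6 into line, so that the three places give one rule.
- Draw the suspected-progression and 4-week samples at the corresponding ferumoxytol MRI visit where possible. Ferumoxytol is given intravenously there in any case.
- Record each draw date relative to the first dose.
- In section 10.0, classify any baseline draw taken after either treatment has begun as on-treatment, with baseline missing. The data are kept, but not as a reference value.

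The cost is about one sentence in each place. The downside is that a few late samples lose their baseline status. The analysis rule can also be applied to samples already taken, provided their draw dates were recorded.
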